12.5 Product Complaint Reporting

It is the responsibility of the investigator to report all product complaint(s) associated with a medical device distributed by Medtronic, regardless whether they are related to intended use, misuse or abuse of the product. Reporting must be done immediately and via the regular channels for market-released products. The reporting of product complaints by the clinical team must be done according to the local Standard Operating Procedures. Medtronic will notify the Regulatory Authorities as applicable for the following incidents immediately upon learning of them and is not limited to AEs and DDs only:

- Any malfunction or deterioration in the characteristics and/or performance of a device, as well as any inadequacy in the labeling or instructions for use which led or might have led to the death or serious deterioration in the state of health of a patient, user, or other person.
- Any technical or medical reason resulting in withdrawal of a device from the market by the manufacturer.
- Any serious deterioration in the state of health, including:
 - Life-threatening illness or injury
 - Permanent impairment of a body function or permanent damage to a body structure

- A condition necessitating medical or surgical intervention to prevent permanent impairment of a body function or permanent damage to a body structure

13. Data Review Committees

No Data Monitoring Committee, Clinical Events Committee or other external committee will be nominated for this study as the study includes no significant interventions (i.e. blood draw only) intended to sustain life or reduce risk of a major adverse health outcome.

14. Statistical Design and Methods

This is a preliminary study aimed at collecting data from enrolled subjects for algorithm development and improvement. Subjects with valid recorded data from the study device (EEG signals) and a completed eCRF will be considered as valid subjects and will be included in the primary analysis.

A statistical analysis plan with detailed statistical procedures and methods will be finalized prior to data analysis. Any changes in statistical methods will be detailed in the Clinical Study Report.

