10.1 Schedule of Events & Data Collection

Table 1. Schedule of Events & Data Collection Requirements

Data	Baseline	Surgery
Informed Consent Process and Documentation	X	
Inclusion/Exclusion criteria evaluation	X	
Demographic & Medical history	X	
Mini Mental State Examination (MMSE)	X	
Mini Nutritional Assessment (MNA-SF®)	X	
Edmonton Frail Scale	X	
Blood sample - levels of albumin, total protein, hemoglobin, total cholesterol	X	
Pregnancy screening (See section 10.6.1)		X
BIS™ sensor and Nellcor™ sensor application		X
BIS™ data collection		X
Patient vital signs (blood pressure, EtCO ₂ , SpO ₂ , pulse rate, FiO ₂ %, EtO ₂ %, respiration rate and temperature)		X
DOA according to the Modified OAA/S Responsive Scale		X
Drug administration during the surgery - Anesthetic drugs, drugs that induced or reduced paralysis, anti-nausea drugs, drugs that reduce pain (drug, dosage and time)	X	X
Adverse Events as described in Section 12		X
Protocol Deviations		X
Reason for Premature Study Termination (including patient death)	X	X

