10.5.4 Blood Samples

Blood sample collection can be completed after informed consent has been obtained. The blood sample can be collected at Baseline, before surgery, or at the start of the surgery visit. If the blood sample is taken after the patient has been sedated and anesthesia induction begins, the blood sample should be taken from the opposite arm from which the intravenous therapy infusion of propofol was administered. The blood sample should be taken as soon as possible, but is required to be taken before intubation or the first surgical incision is made (whichever comes first).

Blood samples to assess the levels of the following will be collected and documented in the eCRF:

- Albumin (gm/dL)
- Hemoglobin (gm/dL)
- Total cholesterol (mg/dL)
- Total protein (gm/dL)

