11.1 Potential Risks

Both the BIS™ monitor system and Nellcor™ system is cleared in the United States, CE marked, AMAR approved in Israel, and used routinely in clinical care to monitor patients. In the routine clinical procedure, the anesthetist uses unilateral sensor, and in some surgeries the BIS™ is part of the monitoring system. For the study, the BIS™ will be used as a standalone monitor with the bilateral sensor. During the surgery, the BIS™ value will be calculated from the left side, as in the routine clinical procedure. The BIS™ device that will be used as study product will be stored outside the operating room after the study procedure. The monitor is being used in accordance with the intended use that has been cleared by regulatory authorities worldwide.

Risks to participation are primarily physical. There are no social, economic, legal, long-term psychological, or other risks that have been identified. Risks under this protocol relate to both study devices and study procedures. The risks from the device(s) are in keeping with the definition of non-significant risk devices. Further, the devices in this study are non-invasive, and the clinical protocol design is minimal risk to the subject. No treatment or treatment decisions will be made during the course of this study. Following is a list detailing potential risks from study devices and the clinical protocol.

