11.1.5 General Anesthetics

Along with the protocol-specified propofol induction period, general anesthesia maintenance will resume per institutional practice as is needed for the surgical procedure.

There are some risks associated with general anesthetics, which should be explained to the patient and covered in the standard surgery clinical consent form. All subjects will be monitored by health care professionals closely for the effects. The most common side effects of general anesthesia include sore throat due to the breathing tube, nausea, vomiting, dizziness, bruising, or soreness from the intravenous therapy drip, shivering and feeling cold, and difficulty passing urine. These may occur despite the best efforts to avoid them.

Also, when placing a breathing tube, there is a small risk that the anesthesia provider can damage the subject's teeth. This risk increases if the subject has loose teeth or other dental problems. With any medication given, the subject could have an allergic reaction. Although rare, unexpected severe complications with anesthesia can occur and include, but not limited to, the remote possibility of infection, bleeding, drug reactions, blood clots, loss of sensation, loss of limb function, paralysis, stroke, brain damage, heart attack or death. The delegated anesthesiologist will be present during the procedure to minimize all risks related to anesthesia.

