12.1 Adverse Events

AE definitions are provided in Table 3. Events related to the surgical procedure including anesthesia administration will not be collected as they related to standard of care practices. AEs will only be collected as they are related to the BIS™ and Nellcor™ devices as well as any device deficiencies as these are commercially released products. All reportable AE information will therefore only be collected beginning at the time of the BIS™ and Nellcor™ sensor placement at the start of surgery and ending when the BIS™ and Nellcor™ sensors are removed.

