12.3 Definitions/Classifications

Where the definition indicates “device”, it refers to BIS™ and/or Nellcor™ devices used in the study.

The influence of age on EEG signals and consciousness during anesthesia (TIARA) Clinical Investigation Plan

Version 5.1

Page 43 of 65

Form

Medtronic

Table 3: Adverse Event and Device Deficiency Definitions (ISO 14155)

Adverse Event (AE)	
Untoward medical occurrence, unintended disease or injury, or untoward clinical signs (including abnormal laboratory findings) in subjects, users or other persons, whether or not related to the investigational medical device and whether anticipated or unanticipated
 
NOTE 1: This definition includes events related to the investigational medical device or the comparator. NOTE 2: This definition includes events related to the procedures involved. NOTE 3: For users or other persons, this definition is restricted to events related to investigational medical devices.

Adverse Device Effect (ADE)	
AE related to the use of an investigational medical device
 
NOTE 1: This definition includes AEs resulting from insufficient or inadequate instructions for use, deployment, implantation, installation, or operation, or any malfunction of the investigational medical device. NOTE 2: This definition includes any event resulting from an error use or from intentional misuse of the investigational medical device. NOTE 3: this includes 'comparator' if the comparator is a medical device.

Device Deficiency (DD)	
Inadequacy of a medical device with respect to its identity, quality, durability, reliability, usability, safety or performance.
 
NOTE 1: DD include malfunctions, use errors and inadequacy in the information supplied by the manufacturer including labeling. NOTE2: This definition includes device deficiencies related to the investigational medical device or the comparator.

The influence of age on EEG signals and consciousness during anesthesia (TIARA) Clinical Investigation Plan

Version 5.1

Page 44 of 65

Form

Medtronic

Seriousness	

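### The device-only adverse-event rule leaves out harm from the study-required blood draw, the draw is missing from the risk list, and the protocol disagrees with itself on whether such an event is reportable

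*Protocol*

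**What the plan says.** **The draw.** Table 1 (Section 10.1) marks "Blood sample - levels of albumin, total protein, hemoglobin, total cholesterol" under Baseline. Section 10.5.4 adds that "Blood sample collection can be completed after informed consent has been obtained". It allows the sample at Baseline, before surgery or at the start of the surgery visit, and no later than intubation or first incision. The blood panel is part of the secondary endpoint (5.1.4). In Section 13 the draw is the only intervention named in the reason for having no committee: "as the study includes no significant interventions (i.e. blood draw only) intended to sustain life or reduce risk of a major adverse health outcome".

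**Collection of adverse events.** The synopsis and Sections 10.7, 12.1 and 15.1 restrict collection to events attributed to the two monitoring devices; all but the synopsis add device deficiencies. Section 12.1 also sets the start: "All reportable AE information will therefore only be collected beginning at the time of the BIS™ and Nellcor™ sensor placement".

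**Definitions and reporting.** Note 2 under the adverse-event definition in Table 3 reads "This definition includes events related to the procedures involved". Table 4 has rows for serious adverse events and for all other adverse events, separate from the rows for device effects.

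**Risks.** Section 11.1 introduces its subsections with "Following is a list detailing potential risks from study devices and the clinical protocol". Section 11.1.5 opens with "Along with the protocol-specified propofol induction period".

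**The concern.** The protocol requires a needle procedure of each subject, and its safety rule then admits only device-related events. If that rule is applied as written, a subject harmed by the draw does not enter the adverse-event counts and percentages planned in protocol Section 14.1 and SAP 7.7. Nor would the event come before the early review of the first 40 subjects, which is meant to confirm that there is no safety concern. A clean table would then reflect the rule and would say nothing about how the draw was tolerated.

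The matter is one of safety capture and of consistent instructions to sites. The BIS, age and depth-of-anesthesia analyses are not affected.

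**Working it through.** The plan states no figure on this point, so the check is a comparison of texts. The only arithmetic is the denominator: one sample per subject for up to 100 subjects gives up to 100 draws, and 0.65 × 100 = 65 of them in subjects over 65.

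**1. Is the draw a study procedure?** The protocol does not say so in one sentence. It is inferred from four facts: the sample follows consent, it has its own line in Table 1, it feeds the secondary endpoint, and Section 13 names it as the intervention. Nothing in the protocol calls it standard of care.

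**2. What does each place admit, and from when?**

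| Protocol place | Events admitted | Window |
|---|---|---|
| Synopsis | Device-related only | Not stated |
| 10.7 | Device-related, plus deficiencies | From enrollment |
| 12.1 | Device-related, plus deficiencies | Sensor placement to sensor removal |
| 12.3.1 | Scope not restated | BIS sensor application to end of surgery |
| 15.1 | Device-related, plus deficiencies | Not stated |
| Table 1 | Refers to Section 12 | Surgery column only |

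Section 10.7 conflicts with 12.1 and 12.3.1 on the start of the window. It is still limited to devices, so the earlier start does not admit a draw-related event.

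**3. Apply this to the draw times that 10.5.4 permits.** Section 10.6.2 puts the BIS sensor on before any anesthetic is given.

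| Time of draw | Inside the 12.1 / 12.3.1 window? | Inside the scope? |
|---|---|---|
| Separate Baseline visit | No | No |
| Day of surgery, before the sensor | No | No |
| After the sensor, up to intubation or incision | Yes | No |

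The scope rule excludes every row. The window excludes only the first two.

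**4. Do the stated reasons for the narrow scope reach the draw?** Two are given in 12.1 and 15.1: the devices are already on the market, and events of surgery and anesthesia belong to ordinary care. A blood sample taken for the study is neither a marketed device nor, on this text, part of routine surgery or anesthesia.

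**5. Are other passages wider?** Yes. Table 3 Note 2 counts procedure-related events as adverse events, and 12.1 sends the reader to Table 3 for its definitions. Table 4 sets deadlines for serious events and for all other events with no device qualifier. A site reading 12.1 would not report a draw-related faint; a site reading Tables 3 and 4 might.

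**6. Is the draw in the risk list?** Sections 11.1.1 to 11.1.5 cover the BIS sensor, the BIS system, the Nellcor sensor, surgery and general anesthetics. The nearest entry is bruising or soreness from the intravenous drip, listed as a side effect of anesthesia. Sections 12.1.1 and 12.3.1 both rely on Section 11 for foreseeable events, so the omission carries forward.

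**7. Is the Section 13 parenthetical accurate?** It names the draw alone. Section 10.6.3 lays down a stepwise propofol induction, and 11.1.5 describes that induction as set by the protocol. The passages disagree.

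**The case against.** The best defense is that the narrow scope is deliberate and explained. The devices are commercial, Table 3 reproduces general ISO 14155 definitions, and a general definition followed by a narrower collection rule is not by itself a contradiction. That is fair as far as it goes. But the explanation covers devices, surgery and anesthesia and leaves the draw unaddressed, and the unqualified rows in Table 4 are reporting instructions, not definitions.

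The other side is right to resist several stronger readings that a reader might infer:

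- **That a draw-related event can never be recorded.** This is not supported. The Table 4 rows could be read to admit one. The exit form in 10.11, required for all subjects, asks for applicable adverse-event or death information. Section 10.10 asks for the status of ongoing events at withdrawal, and Table 1 takes the reason for premature termination at Baseline too. The text of Section 12.4 was not available for this check. What is shown is exclusion under the rule in 12.1 and 15.1, together with inconsistency elsewhere.
- **That every draw falls before the window.** Section 10.5.4 permits draws after the sensor is on.
- **That the decision to have no committee collapses.** Section 13 rests on the absence of interventions meant to sustain life or lower the risk of a major adverse outcome. Neither the draw nor the induction is presented as having that purpose, so naming the induction would leave the stated reason standing.
- **That a number of missed events can be given.** No event rate for the draw appears in either document, and a chosen rate multiplied by 100 would only restate the choice.

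The consent form was also not available, so it may mention the draw. The point here concerns the protocol's own risk list.

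**Conclusion.** The point holds as a defect of scope and consistency. Under the collection rule repeated in four places, an event caused by the study blood draw is out of scope at any time, and for draws taken before sensor placement the window excludes it as well. Tables 3 and 4 point the other way. The risk list omits the draw although it claims to cover the clinical protocol, and the Section 13 parenthetical does not match 10.6.3 and 11.1.5.

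In size this is minor. It touches up to 100 draws, and the number and severity of events are unknown; in my judgment most would be mild. The conclusion assumes that the draw is study-specific, which the text implies but does not state, and that sites follow 12.1 where it conflicts with the tables. It does not bear on whether a committee is needed.

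**What to change.** - **Scope and window.** In the synopsis, 10.7, 12.1, 12.3.1, 15.1 and Table 1, add events related to the study blood draw, collected from the time of the draw. All six need the change; editing only some would create new conflicts.
- **Reconciliation.** Settle the start of the window between 10.7 and 12.1/12.3.1, and bring the scope into line with Table 3 Note 2 and the two unqualified Table 4 rows.
- **Risk list.** Add blood sampling to Section 11.1, so that the references in 12.1.1 and 12.3.1 work.
- **Section 13.** Correct the parenthetical to agree with 10.6.3 and 11.1.5.
- **Induction.** State whether events of the induction laid down by the protocol fall under the standard-of-care exclusion in 12.1 and 15.1. The passages must be reconciled; this point does not prejudge the answer.

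The cost is protocol wording, a relatedness option for the draw on the adverse-event form, and an occasional extra form. SAP 7.7 already allows summaries by relationship, so no new analysis is required. No committee or visit is added. If the sponsor decided to collect induction events as well, the workload would be greater, and that should be weighed separately.

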14.1 Sample Size Justification

Up to 100 subjects will be enrolled in the study, with 65% subjects over the age of 65 years. The sample size estimate was not based on hypothesis testing. The primary objective is to evaluate the age impact on the relationship between the BIS score and the depth of anesthesia. The sample size is not powered to detect a statistically significant difference as this study is a feasibility study. Statistical Methods

Descriptive statistics will be used to summarize study outcomes. Subjects with valid recorded data from the study device (EEG signals) and a completed eCRF will be included in the primary analysis.

The relationships between BIS parameters, age, physical and cognitive state, and depth of anesthesia in patients undergoing surgery under general anesthesia will be assessed. Pearson's correlation or Spearman's rank correlation will be calculated as appropriate. Continuous variables will be evaluated using analysis of variance (ANOVA) or nonlinear E_{max} model, and categorical variables will be evaluated using the chi-square or Fisher's exact test, as well as multivariate logistic regression with age as an explanatory factor. A P-value of less than 0.05 is considered statistically significant unless otherwise specified.

An early data review will be performed for the first 40 enrolled subjects to ensure data validity and no safety concern. Sample size re-estimation may be performed to ensure sufficient data to be collected to meet the study objectives.

For safety assessments, AEs will be summarized using frequency counts and percentages. Descriptive summary will be provided by severity and relationship as needed.

15. Ethics

15.1 Statement(s) of Compliance

The MDT18067TIARA study will be conducted in full conformity with this study protocol, with its ethical principles having origin in the Declaration of Helsinki. TIARA was designed to reflect the GCP principles outlined in the latest version of ISO 14155 and other international clinical requirements outlined below. These include the protection of the rights, safety and well-being of human subjects, controls to ensure the scientific conduct and credibility of the clinical investigation and the definition of responsibilities of the sponsor and investigators. In accordance with ISO 14155, the sponsor shall avoid improper influence on, or inducement of, the subject, monitor, any investigator(s) or other parties participating in, or contributing to, the clinical investigation. All investigators shall avoid improper influence on or inducement of the subject, sponsor, monitor, other investigator(s) or other parties participating in or contributing to the clinical investigation. AE and DD handling in the TIARA study is ISO 14155 compliant for all participating geographies. As the ISO 14155 AE collection requirements are focused on pre-market release studies, AEs will only be collected as they are related to the BIS™ and Nellcor™ devices as well as any device deficiencies as these are post-market or commercially released products. USADE assessment is not applicable for this reason. Events related to the surgical procedure including anesthesia administration will not be collected as they related to standard of care practices.

Ultimately, all study sites in all geographies will follow and comply with:

- The CTA
- The procedures described within this CIP
- Local IRB/EC/HC Requirements

No study procedures at the site will be performed until the governing IRB/EC/HC provides approval. Any action that is taken by the local IRB/EC/HC with respect to this study will be forwarded to the sponsor as soon as possible.

In addition to the regulatory requirements outlined above, the study will be conducted according to federal, national and local laws, regulations, standards, and requirements of the countries/geographies where the study is being conducted. These include but are not limited to:

- In Europe the study will be conducted in compliance with the DoH version 2013.

The study will be publicly registered in the US prior to any enrolments in accordance with ISO 14155 on <http://clinicaltrials.gov>. In addition, the study may be registered in local regulatory databases where required by local law including the Israel Ministry of Health website for clinical trials at <https://my.health.gov.il/MyPortal/CliniTrials/Pages/Editor.aspx>. For the Netherlands, it is expected that the study may be listed at www.rijksoverheid.nl/mensenonderzoek. Requirements for each region will be confirmed once sites are selected.

Approval of the CIP and CIP amendments is required from the following groups prior to any study procedures at a study site:

- Medtronic
- Principal Investigators (where required by local law/regulations)
- Geography-specific regulatory authorities (if regulatory approval is required)
- An independent medical IRB/EC/HC

16. Study Administration

16.1 Monitoring

It is the responsibility of Medtronic to ensure proper monitoring of this study. Trained Medtronic personnel or delegates appointed by Medtronic may perform study monitoring at the study site or remotely in order to ensure that the study is conducted in accordance with the CIP, the CTA, and the applicable regulatory and local requirements. Medtronic, or delegates, must therefore be allowed access to the subjects' case histories (i.e. clinic and hospital records, and other source data/documentation) upon request as per the ICF, Research Authorization (where applicable) and CTA. The PI should also be available during monitoring visits, as detailed in the monitoring plan, to review together with the monitor the visit outcomes and general study progress.

